#### **Inclusion and Exclusion Criteria:**

Women will be recruited from the antenatal clinic if they are:

##### **Inclusion criteria.**

- Between 18 and 40 years old
- In their first trimester with an uncomplicated singleton pregnancy of less than 19 weeks
- Self-identify as either Black or Hispanic
- Speak and read English or Spanish

##### **Exclusion criteria**

Women will be excluded if they have:

- Chronic medical conditions (e.g., hypertension, or diabetes)
- Currently receiving treatment or therapy for a psychiatric diagnosis

07/30/2021

- Have participated in this study with a prior pregnancy
- Obstetrical complications, such as preeclampsia, gestational diabetes, or fetal abnormalities
- Do not speak and read English or Spanish

**Recruitment.** Research team members will approach women in the antenatal clinic who may be eligible for the study based on their chronological age and fetal gestational age and verbally explain the study. Gestational age is based on the ultrasound dating or last menstrual period when ultrasound is not available. If a woman self identifies as Black or Hispanic, a participant informed consent form will be provided and consent obtained. A copy of the participant informed consent form will be given to the participant. She will then be screened for study eligibility.

## Measures

**General Anxiety Scale (GAD-7):** is a 7-item, 4-point Likert-type scale ranging from (0) Not at all to (3) Everyday, that assesses the participants' level of anxiety over the last 2 weeks. Scores range from 0 to 21, with higher scores indicating greater functional impairment related to the patient's experience of anxiety. The scale's reliability and validity have been tested across clinical care settings. It has been found useful in monitoring symptom severity and changes across time. Brevity of the GAD-7, (it can be completed in 5 minutes or less) helps to minimize patient burden. In our COPE-P pilot work, the Cronbach's alpha was .89.

**Perceived Stress Scale (PSS):** is a widely used, standardized measure of global stress designed to elicit the degree to which respondents find their lives unpredictable, uncontrollable, and overloading (three central components of stress). Concurrent and predictive validity were supported by comparing the PSS with depression scores and life-event scales in college samples. The PSS has demonstrated internal consistency reliability of .84 to .86 with young adult populations and .80 with pregnant minority women and takes about 5 minutes to complete. Cronbach's alpha in the COPE-P pilot was .80.

**The Edinburgh Postnatal Depression Scale (EPDS):** is a 10 item self-report perinatal depression questionnaire. The scale asks participants to describe how they have felt in the previous week. Unlike other depression screening tools, the EPDS excludes questions regarding somatic symptoms of pregnancy and has been found to be equivalent to a structured interview in determining prevalence of depression. Scores range from 0-30 with higher scores signifying higher severity of depressive symptoms. ACOG supports the EPDS as a depression screening tool in pregnant women because of its brevity, readability and scoring ease. As will be indicated in participant informed consent forms, if a woman answers item 10 (self-harm) with a 1,2, or 3 she will be accompanied to a mental health provider for immediate care. Women with high scores will be referred to their primary care provider and we will monitor to assure follow up. The EPDS takes 5 minutes to complete.

**24 Hour Adult Nutrition Log:** Nutrition will be examined by conducting a 24 hour diet recall for each participant at each data point. Food models and pictures will be used to accurately identify portion sizes and participants will be asked brand names of food. The target day for the diet recall will be 24 hours in advance of the data visit. Information from the diet histories will be analyzed using the Food Processor database that contains over 2400 foods. Nutrient values are in accord with information provided by the United States Department of Agriculture and over 550 other research sources. Fast foods are included as are over 1182 convenience food items. The database is updated annually.

**Healthy Lifestyle Beliefs Scale:** The HLBS is a 16-item scale adapted from other belief scales used by Co-PI [name] in prior studies and takes 5 minutes to complete. This scale taps beliefs about various facets of maintaining a healthy lifestyle (e.g., "I believe that I can be more active" and "I am sure that I will do what is best to lead a healthy life"). Subjects respond to each item on a five point Likert-type scale that ranging from 1 strongly disagree to 5 strongly agree. Construct validity of the scale has been supported through factor analysis with over 1000 young adults. Cronbach's alpha from the COPE-P pilot was .91.

**Healthy Lifestyle Behaviors Scale:** Healthy lifestyle behaviors will be measured with the Healthy Lifestyle Behaviors Scale developed for use in multiple prior studies. Subjects respond to each of the 15 items (e.g., I exercised regularly; I talked about my worries) on a 5-point Likert-type scale that ranges from 1 strongly disagree to 5 strongly agree. Construct validity has been supported through factor analysis from data obtained in our prior work. Cronbach's alpha in the COPE-P pilot was .86 and took 5 minutes to complete.

**Exercise:** During pregnancy, spring loaded pedometers have been found to be inaccurate due, to the pedometer being tilted away from the vertical plane such that the spring suspended lever arm does not register

all steps. This is particularly true for overweight or obese pregnant women so an accelerometer measure of step counts is much more accurate. However, accelerometer type measures of physical activity may over count steps especially when participants are involved in motor vehicle traffic and most especially on bumpy roads. Devices, such as the Fitbit Flex 2, combine accelerometer and pedometer features to improve accuracy and have the advantage of being worn on the wrist like a bracelet so women are less likely to forget to use it, a common problem with devices that necessitate being affixed to clothing.

**Birth and Post-Natal Outcome Data:** will be abstracted from clinic charts by team members blinded to treatment group and from the Demographic and Personal Information Form (DPI) completed at T0-T3.

**COPE-P Acceptability:** Measures acceptability in 5 minutes at a 6th-grade reading level.

**Group Prenatal Care Acceptability:** The Group Prenatal Care Acceptability asks participants to describe aspects of their Group Prenatal Care experience on a scale of 1-5 and if they found it helpful. It takes 3-5 minutes to complete.

**COPE-P/PregnancyPlus Program Evaluation:** The Program Evaluation will collect open-ended responses from participants evaluating their experience with the COPE-P and the PregnancyPlus program. The survey will take approximately 5-7 minutes to complete.

**Table 1. Study Variables, Measures and Timing**

Variables	Measures	Timing
Demographic Characteristics Age, Height Education Level, Relationship Status, Race/Ethnicity, Language Spoken, Income, Parity, Medications, Mental Health Referral/Rx post screening	Demographic and Personal Information (DPI) Form	T0 =Baseline (screening visit) T1 = 31 weeks T2 = 6-8 weeks postpartum visit T3 =6 months well baby visit
Healthy Lifestyle Behaviors	Healthy Lifestyle Behaviors Scale 	T0, T1, T2, T3
Healthy Lifestyle Beliefs	Healthy Lifestyle Beliefs Scale 	T0, T1, T2, T3
Nutrition	24 Hour Nutrition Log/Food Processor	T0, T1, T2, T3
Weight Gain/Loss, BMI	Scale	T0, T1, T2, T3
Exercise	Steps Fitbit Flex 2 Accelerometer	T0 (given at screening T1, T2, T3)
Psychosocial Health		
Anxiety	GAD7	T0, T1, T2, T3
Depressive Symptoms	EPDS	T0, T1, T2, T3
Perceived Stress	PSS	T0, T1, T2, T3
Birth and Post-Natal Outcomes	Infant Data Form	
Gestational Age at birth, Gender	Chart review	Post delivery
Birth Weight, Birth Length, Overall Health	Chart review	Post delivery
Mode of Delivery (C/S, Vaginal, Forceps/Vacuum)	Chart review	Post delivery
Breastfeeding (initiation and duration)	DPI Form	T2, T3
COPE-P Acceptability	Index (COPE-P group)	T1 and T2
Group Prenatal Care Acceptability	Group Prenatal Care Acceptability	T1
Program Experience	COPE-P/PregnancyPlus Program Evaluation	T1 and T3

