## Research Protocol: Healthy Lifestyle Prenatal Care Study

### Aims:

**Specific Aim 1.** Use a RCT to evaluate the short- and more long-term efficacy of the COPE-P program to improve healthy lifestyle behaviors (nutrition and exercise), psychosocial health, and birth and post-natal outcomes in pregnant emotionally distressed minority women as compared to an attention control group.

**Hypotheses 1a (primary outcomes).** Immediately after the COPE-P program, at 4-6 weeks postpartum (3 months post intervention), and at 6 months postpartum (8 months post intervention), COPE-P participants will report higher healthy lifestyle behaviors, and less anxiety, stress and depressive symptoms than will the attention control participants.

**Hypothesis 1b (secondary outcomes).** COPE-P participants will demonstrate more appropriate pregnancy weight gain, better birth outcomes (mode of delivery, birth weight, and gestational age), more appropriate postpartum weight loss, and better breastfeeding outcomes than attention control participants.

**Specific Aim 2.** Examine the role of cognitive beliefs and perceived difficulty in leading a healthy lifestyle in mediating the effects of the COPE-P program on healthy lifestyle behaviors and psychological symptoms in minority pregnant women.

**Hypothesis 2 (theory building exploratory).** The effects of the COPE-P program on participants' healthy lifestyle behaviors and levels of anxiety, stress and depressive symptoms will be mediated by beliefs about their ability to make healthy lifestyles choices and their perceived difficulty in leading a healthy lifestyle.

**Exploratory Aim.** Explore characteristics that may moderate healthy lifestyle behaviors, psychosocial health, and birth and post-natal outcomes (e.g., race/ethnicity, income, age, parity, language, level of education, marital status).

**Research Question:** What is the short and long-term effect of the COPE-P program in high-risk pregnant minority women receiving prenatal care on healthy lifestyle behaviors (nutrition and exercise), psychosocial health (healthy lifestyle beliefs, healthy lifestyle behaviors, anxiety, stress and depression), and birth and post-natal outcomes (gestational age at birth, gender, birth weight, birth length, overall health, mode of delivery, breastfeeding (initiation and duration) versus an attention control group (PregnancyPlus group).

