**Overview of the design.** The study conducted will be a longitudinal randomized block RCT with repeated measures (beginning with screening prior to 19 weeks, group prenatal care in both groups (COPE-P intervention group and PregnancyPlus attention control group) from  $16 \pm 2$  to  $31 \pm 2$  weeks and ending at 6 months postpartum). We will block on race/ethnicity to ensure equal numbers of Hispanic and Black women in the COPE-P and PregnancyPlus groups. There will be a total of 30 groups over the course of the study. There will be 22 English speaking groups and 8 Spanish-speaking groups. We will consent and screen up to 700 women, knowing that approximately half will screen out. In order to achieve our target of 182 Black or Hispanic women who complete the study, and accounting for a 30% attrition rate, we will enroll up to 236 women who screen in at Jacobi Medical Center. Four groups (of at least six women per group) will run in each 18-week time segment (COPE-P intervention is six sessions each three weeks apart). The PregnancyPlus group also will have six group prenatal care sessions each three weeks apart. Each session is 1 hour and 30 minutes to 1 hour and 45 minutes in length. Each group within the 18-week time segment will be randomly assigned (using a sealed envelope technique) as either a COPE-P or PregnancyPlus group. At Jacobi Medical Center in Bronx, NY, for each 18-week time segment, there will be two control groups and two intervention groups. The intervention and attention control groups programming will be delivered in Group Prenatal Care methodology which begins in the second trimester consisting of at least 6 women per group. Participants (18 – 40 years) will be screened prior to their 19th week of pregnancy and recruited into the study from the antepartum clinic.

If a participant does not screen into the study, she will be thanked for her time and interest and paid \$10.00 for her participation in the screening process.

07/30/2021

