**PregnancyPlus Attention Control Group:** At each group session, the PregnancyPlus attention control group will receive the prenatal care described under standard care performed by certified nurse midwives. Additionally, each week for six weeks, they will discuss a pamphlet designed for patient education by ACOG. These six pamphlets are: 1) Nutrition during pregnancy 2) Exercise during pregnancy 3) Obesity and pregnancy 4) Exercise after pregnancy 5) Breastfeeding your baby 6) Routine Tests during Pregnancy. At each group prenatal care session, routine obstetric assessment (blood pressure, pulse, weight, BMI, urinalysis for glucose and protein, auscultating fetal heart tones, and uterine size assessment) will be performed. Routine discomforts of pregnancy, smoking cessation, and danger signs of pregnancy will be discussed. Women will return to receiving individualized standard prenatal care at the end of the 6 sessions. [name] will conduct the training of the attention control group midwives and [name] will conduct the training of the intervention group midwives. The same protocol for assessing fidelity will be used for COPE-P and PregnancyPlus.

Different care providers will run the COPE-P and PregnancyPlus groups, assuring that there is no carryover effect of the intervention into the control group.

In addition to baseline assessments, at the end of the 18-week timeframe and at their last group prenatal care session, all women will complete the GAD-7, PSS, EPDS, a 24 hour diet recall, the Healthy Lifestyle Behaviors Scale and the Healthy Lifestyle Beliefs Scale. Fitbit data and weight also will be obtained. In the intervention group, participants also will complete the COPE-P evaluation. This data will be **T1**, and will be collected at approximately 31 weeks gestational age. For women who miss this visit, data will be collected at the next scheduled prenatal visit. Participants will be compensated \$30 for their study participation.

Three months after the intervention (approximately 4-6 weeks postpartum - **T2**), all women will be contacted and will once again complete all measures, as well as an infant data form, at the routine postpartum visit. Participants will receive \$40.00 for their participation.

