At eight months post intervention (**T3** - six months postpartum at the six-month well baby visit), all women will once again be contacted and complete all measures (including weights taken on available pediatric clinic adult scales –same model as prenatal scales). Participants will receive \$50.00 for their participation. Outcome data from charts will be collected by team members blind to group assignment.

If study visits cannot be conducted face-to-face, data will be collected through telehealth methods such as via phone or video call (Zoom or Facetime etc.).

**Sampling.** Women will be recruited from the antenatal clinic if they are: between 18 and 40 years old, in their first trimester with an uncomplicated singleton pregnancy of less than 19 weeks, and self-identify as either Black or Hispanic and can read and speak English or Spanish. A completed sample size of 182 Black and Hispanic women from JMC in the Bronx and 182 Black and Hispanic women from OSU Total Health and Wellness clinics will be required to meet the determined sample size of 364 total (at 4 data collection points for each, resulting in ~1,450 observations). This will have greater than 80% power to detect small to moderate effects (i.e. 25 or greater) between group differences in healthy lifestyle behaviors, psychosocial health, and outcomes testing at alpha = .05 for all proposed models. The sample of 364 will have > .80 to detect a small to medium mediated effect. The sample of 364 will have > .80 to detect a small to medium mediated effect.

**Setting. Jacobi Medical Center** is part of New York City Health + Hospitals (NYC H + H), the largest municipal hospital system in the United States. New York City Health + Hospitals oversees the public health care system in all the five boroughs that comprise New York City. It provides one-fifth of the total number of discharges and more than one-third of the emergency services and hospital-based clinic visits in all of New York City. Jacobi Medical Center is an academic affiliate of the Albert Einstein College of Medicine. Jacobi Medical Center is located in the Bronx. As one of the largest health care delivery facilities in the Bronx and in New York City, Jacobi Medical Center has developed a world- wide reputation of distinction. It is renowned for its primacy in

07/30/2021

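### Table 1 takes breastfeeding initiation from the DPI form at T2 and T3, so a woman reached at neither visit has no observed value for an event around birth, although charts are already abstracted blind for the neighbouring birth outcomes

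*Combined protocol and SAP*

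**What the plan says.** Hypothesis 1b (Aims) makes breastfeeding part of the secondary outcomes: COPE-P women are expected to show "better breastfeeding outcomes than attention control participants".

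Table 1 is the only place where individual outcomes are matched to a source and a time. It lists "Breastfeeding (initiation and duration") as a single row, with the DPI form as the measure and T2 and T3 as the times. The rows just above it, including "Mode of Delivery (C/S, Vaginal, Forceps/Vacuum"), are assigned to chart review after delivery.

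Four other places bear on the point:

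- Measures, Birth and Post-Natal Outcome Data: these data "will be abstracted from clinic charts by team members blinded to treatment group and from the Demographic and Personal Information Form". No item is assigned to either source.
- The description of T3, repeated under Procedure: "Outcome data from charts will be collected by team members blind to group assignment".
- The description of T2: all women are to "complete all measures, as well as an infant data form, at the routine postpartum visit". Table 1 also names the Infant Data Form beside the heading of the birth and post-natal block. Data may be collected by telehealth when a visit in person is not possible.
- Overview of the design: up to 236 women are enrolled at Jacobi for 182 completers, "accounting for a 30% attrition rate".

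The Analysis plan specifies intention to treat for all analyses and multiple imputation where appropriate. It has no rule specific to breastfeeding.

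**The concern.** Initiation and duration are different kinds of outcome. Duration can be known only by following the woman. Initiation is fixed around birth and belongs in time with gestational age, birth weight and mode of delivery. Table 1 nevertheless ties it to postpartum contact.

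Two things are at stake. The first is avoidable missing data. A woman reached at neither T2 nor T3 has no observed value, and imputing one relies on assumptions about non-returners that an observed value would not need. The sample is selected for anxiety, stress or depressive symptoms, so women who do not return may well differ from those who do. The second is the quality of the source. Chart abstraction is stated to be blind. The follow-up questionnaires are administered by a research team member, and blinding is not stated for that step.

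**Working it through.** **1. Source and timing, side by side**

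| Item | Source in Table 1 | Time in Table 1 | Needs postpartum contact? |
|---|---|---|---|
| Gestational age, birth weight and length, mode of delivery | Chart review | After delivery | No |
| Breastfeeding initiation | DPI form | T2, T3 | Yes |
| Breastfeeding duration | DPI form | T2, T3 | Yes, necessarily |

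The Infant Data Form does not close the gap, because the text has it completed at the T2 visit. The Measures entry does not rule out the chart for breastfeeding, but it does not assign it either. Staff working from Table 1 would not abstract it.

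**2. The plan's own attrition figure**

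- 182 × 1.30 = 236.6, which matches the stated 236.
- The usual inflation, 182 / (1 − 0.30) = 260, does not match. With 30% attrition, 236 × 0.70 = 165 would complete.
- Exactly 182 completers out of 236 means 54 lost, or 54 / 236 = 23%.

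Attrition is counted to study completion at six months postpartum, and its timing is not given. Let L be the share of women reached at neither T2 nor T3. L is an assumption, and planned attrition caps it at 30%.

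**3. Women without an observed value, and loss of precision**

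The number missing at Jacobi is 236 × L. If women are treated as independent, the standard error of a difference in proportions grows by 1 / √(1 − L).

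| L (assumed) | Missing of 236 | Standard-error ratio | Increase |
|---|---|---|---|
| 10% | 24 | 1 / √0.90 = 1.054 | 5% |
| 20% | 47 | 1 / √0.80 = 1.118 | 12% |
| 30% (ceiling) | 71 | 1 / √0.70 = 1.195 | 20% |

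**4. Allowance for group randomisation**

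Groups are randomised, and the variance of an arm's rate is proportional to [1 + (m − 1)ρ] / m for m women per group and intraclass correlation ρ. Assume m = 8 (the plan says at least six), falling to 5.6 at 30% loss.

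- ρ = 0.02: √[(1.092 / 5.6) / (1.14 / 8)] = 1.17, an increase of 17%.
- ρ = 0.05: √[(1.23 / 5.6) / (1.35 / 8)] = 1.14, an increase of 14%.

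The figures in step 3 are therefore upper values.

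**5. Possible bias**

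Suppose lost women initiate less often than retained women by the same gap in both arms. The observed difference is then biased by (difference in L between arms) × gap. With losses of 10% and 30% and a gap of 10 to 30 points, that is 0.20 × 10 = 2 points to 0.20 × 30 = 6 points. With equal losses it is zero. All these inputs are assumptions.

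**The case against.** The plan has a fair defence. Maternal report within weeks of birth is a reasonable way to record initiation, and it avoids differences in how charts code feeding. Women are contacted again at T3, telehealth is allowed, and imputation is available. The Measures entry already mentions charts.

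Much of this stands, and it rules out several stronger readings that a reader might infer:

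- *Every woman lost before T2 goes unscored.* Not so. T3 also collects the item, so the gap covers only women reached at neither visit. Those seen only at T3 would report from memory at about six months.
- *The chart would recover everyone.* The documents do not say that the abstracted charts record infant feeding. Nor do they say that charts remain available after withdrawal, transfer of care or delivery elsewhere.
- *The trial would lose a full 30% on this outcome.* That requires all planned attrition to fall before T2, with none of those women returning at T3.
- *Power would fall from 78% to 67%.* That is the result for assumed initiation of 75% versus 85% with 236 and then 182 women per arm. It is a 23% loss, assumes that both sites enrol 236 and that charts recover every lost woman, and ignores group randomisation.
- *The plan analyses completers only.* It does not; intention to treat is stated for all analyses.

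What the defence does not answer is that no part of the document gives a delivery-time source for initiation, and that the Measures entry and Table 1 leave the source unclear.

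**Conclusion.** The point holds in a limited form. As Table 1 stands, initiation is unobserved for any woman reached at neither T2 nor T3, although charts are already to be abstracted blind for the outcomes listed beside it. The cost in precision is at most about 5%, 12% or 20% of the standard error at 10%, 20% or 30% loss. Bias is possible but cannot be sized from the documents.

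The benefit of a change rests on two things not shown: that charts record feeding, and that they can be reached for lost women. The point touches one component of a secondary outcome and no primary outcome. It is a minor improvement worth making because it is cheap, not an error that threatens the trial.

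**What to change.** Split the Table 1 row in two:

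- *Breastfeeding initiation:* blind chart review after delivery where the chart records infant feeding, using one common definition across sites; DPI form at T2 (or T3) when the chart is silent or unavailable.
- *Breastfeeding duration:* DPI form at T2 and T3.

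Amend the Measures entry on birth and post-natal data to say which items come from which source, in line with the table. Before adopting the change, confirm at each site that feeding is recorded in the charts to be abstracted.

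The cost is one more field on an abstraction already planned, with no extra visit or burden on participants. The small downside is the work of harmonising chart coding across sites.
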